5.6 Mistakes made in clinic flow and diagnosis & care procedures

We will highlight mistakes made during the study in table below; for each mistake, we will try to investigate at what point in the clinic flow the mistake was made (at clinician-level, laboratory-level or diagnosis and care-level). The WISH procedures results will be taken as a reference, as these were the ones dictating the clinic flow. Where necessary, specifications of the mistakes committed will be made in footnotes.

General	N = 705
POC tests erroneously ordered from laboratory by clinician N	
- UTI tests erroneously requested N	

- Syphilis tests erroneously requested N	
- Pregnancy test erroneously requested N	
POC tests erroneously not ordered from laboratory by clinician N	
- UTI tests erroneously not requested N	
- Syphilis tests erroneously not requested N	
- Pregnancy test erroneously not requested N	
Sample erroneously not taken by clinician N	
- EcoCare pH swab erroneously not taken N	
POC tests erroneously performed by laboratory (while not ordered by clinician) N	
- UTI test erroneously performed	
- Pregnancy test erroneously performed	
POC tests erroneously not performed by laboratory (while requested by clinician) N	
- UTI test erroneously not performed	
- Pregnancy test erroneously not performed	
Treatment erroneously given N	
- Ciprofloxacin 500 mg single dose given	
Treatment erroneously not given N	
- No treatment given for BV diagnosis	
- No treatment given for candidiasis diagnosis	
Partner notifications missed N	
Partner notifications performed incorrectly N	
Referrals erroneously made N	
Referrals erroneously not made N	

Abbreviations: POC test = point of care test.

6. Additional laboratory results

Additional tests were performed on vaginal swabs and urine to perform sensitivity analyses and to gather more data for hypothesis-generating exploratory analyses; however, these tests are not gold standard tests. As previously described, unless opted out for, all women handed in two vaginal swabs for sensitivity analyses and (again unless opted out for) long-term storage. After performing UTI and/or pregnancy testing during the Main Visit, urine was centrifuged and the pellet was stored in two cryovials of 2 ml each, at -80 degrees Celsius. Participants who did not undergo any urine testing did not have urine stored.

Vaginal swab results	n (%) N = xxx
Mycoplasma genitalium qPCR result: - Positive	
Mycoplasma hominis qPCR result [If performed by ITM] n (%): - Positive	
Urine results	n (%)
	N = xxx
E. coli qPCR result n (%): - Positive	
P. mirabilis qPCR result n (%): - Positive	
Lactobacillus genus qPCR log ₁₀ meq/ml: median [SD]	
Lactobacillus crispatus qPCR log ₁₀ meq/ml: median [SD]	

7. Feasibility endpoints

To show it is possible to implement improved urogenital infection care service, in this section, we will report M&E indicators such as inputs (procurement experiences, infrastructure/training experiences) and outcomes/impacts (improvements of access to and quality of services).

7.1 Infrastructure/training/procurement: requirements and challenges

The RU clinic was already in place prior to beginning the study, and had experience offering urogenital care to Rwandan at-risk women. To implement the WISH procedures, several changes in infrastructure and training had to be implemented.

Торіс	Already in place	Had to be	Challenges	Comments
		established	experienced	
Infrastructure & laboratory	 Equipped basic air- conditioned laboratory Fully equipped clinic rooms -80° C freezers for storage, fridges already available 	 Installation of GeneXpert platform with desk computer Internal quality control measures had to be devised to test POCT Pharmacy-like room at RU's premises to store medications dispensed 	 GeneXpert can only be installed with help of technician All POCT have been validated, but which degree of quality control to perform is debatable 	 Installation of GeneXpert is included in price Most Rwandan health centres have a pharmacy on premises Quality control could also be organized centrally (at LNR) if WISH procedures were to be implemented -80° C freezers only used for research- specific procedures
Consumables	 HIV testing materials all available locally All clinic consumables are available locally All types of medication used in WISH are available in local pharmacies 	 GeneXpert CT/NG cartridges had to be imported TV OSOM test and syphilis POCT could be ordered locally (but are imported) EcoCare pH swab had to be ordered abroad and imported 	 TV OSOM test can only be ordered in bulk (450 or more) No adequate pH strip for BV testing available locally; cannot currently be ordered in Rwanda 	 HIV rapid testing is already commonplace in Rwanda Procurement problems did not lead to a delay in participant enrolment & testing Ordering pH strips from Rwanda might be possible in government setting
SOPs	- Clinic-specific SOPs were in place (used in RU's previous studies), such as counselling, partner notification, STI management guidelines.	 Existing SOPs had to be updated SOPs had to be (re)written for all POCTs including GeneXpert testing STI treatment SOP was updated to incorporate WISH procedures 	 Difficulty establishing best- practice partner notification due to little experience locally Window periods of STIs (for partner notification) taken from international literature but sometimes difficult to identify partners 	 STI management SOPs now incorporate how to treat depending on method of diagnosis (POCT, syndromic management). More research evidence is needed to improve partner notification programs

Training	Dil staff had	Dillahoratory staff	Clinic flow took o	Full training for
Training		- RU laboratory stall		- Full training for
	experience with most	needed training in	few months to	procedures took about
	clinic procedures	POCT procedures,	implement	3-4 weeks in total;
	- RU staff had some	including GeneXpert	correctly	- CT/NG GeneXpert
	experience with	- RU clinic staff	- Speed in clinic	training for laboratory
	partner notification but	needed training in	flow (especially	technicians took 2 days
	success in past was low	clinic flow, sample	informed consent	 Procedures were well
		collection and	procedures and	implemented
		sample handling	interview)	throughout study
			remained a	
			problem	
			throughout study	
(Local) STI	- WHO and Rwandan	- RU physicians had	- While local STI	- No system currently
guidelines	STI guidelines are	to be trained to	guidelines are in	in place to monitor
0	available and in place	correctly identify	place, some parts	antibiotic resistance
	- Rwandan STI	syndromic	of algorithms (e.g.	and treatment success
	guidelines offer	management	CT/NG risk scoring)	- Ability of Rwandan
	possibility of	diagnoses	are open to	clinics in reaching
	presumptive STI	anaBrioses	- STI guidelines	asymptomatic FSWs is
	treatment for		contain little	unknown but likely low
	asymptomatic ESW/s		information on	- Pwandan VDS
	asymptomatic i Sws		how to identify and	- Kwalidali VDS
			now to identify and	guidennes presume
			notify partners	
				cervical from vaginal
				discharge, which is
				unlikely to be possible
Recruitment	- General recruitment	- Recruitment plan	- First recruitment	- Recruitment was
	SOP was in place but	was written to be	sessions resulted in	successful, with 705
	not specific to WISH	able to recruit at	high number of	participants included in
	study	least 500	FSWs	less than a year
	- RU had a network of	participants during	- Recruitment plan	- See, for more
	community mobilizers	study follow-up	had to be amended	information, section
	that help with		twice to obtain a	7.2
	recruitment and		good sample of	
	sensitizing		Kigali's population	

Abbreviations: CT = *Chlamydia trachomatis*; FSW = female sex worker; LNR = national reference laboratory of Rwanda; NG = *Neisseria gonorrhoeae* STI = sexually transmitted infection; SOP = standard operating procedures; TV = *Trichomonas vaginalis*; VDS = vaginal discharge syndrome.

7.2 Recruitment challenges

705 participants were enrolled in the WISH study between July 2016 to March 2017. Some challenges were observed by the RU Outreach Manager and the PI during the recruiting period. These include:

- Most women interviewed are not aware that urogenital infections can be asymptomatic as well. Moreover, there is not a culture of seeking preventive care; it is only when women have (severe) symptoms that they seek care.
- Some women avoid care due to long waiting times at local clinics; some go to pharmacies directly to request treatment, without getting diagnosed.
- Women complain that their urogenital symptoms often do not resolve (due to misdiagnoses, reinfection or treatment failure). Therefore, they decide not to return to the clinic.
- Some women may believe that traditional medicine provides a better cure rate than "Western"

medicine.

- Despite free diagnostics and treatment provided at RU, some women struggled with high transport cost and/or time lost due to not being able to work.
- Specific to clinical research, recruitment was sometimes difficult do to misconceptions about study participation and rumours spread in local communities.
- Taboos related to sexual care and sex in general; more specifically, women might be blamed when informing their partner(s) of diagnosed STIs and therefore either not participate in the study, or, when participating, to be inclined not to notify their partner(s).

Even though some of these challenges are specific to the situation of RU, some problems might be faced by urogenital clinics and health clinics in other parts of sub-Saharan Africa as well. In general, we have shown it is feasible to recruit women who are asymptomatic, or who have symptoms but who have not presented to local health clinics. However, the experiences during the WISH study do show that it is essential to provide good counselling, and to seek support from community mobilizers and authorities to reach the women at (high) risk for STIs.

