1.1 WISH objectives and endpoints

The current standard of care for urogenital infections in Rwanda is syndromic management. Many urogenital infections are asymptomatic and therefore completely missed, and the management of vaginal discharge syndrome (VDS) is known to be suboptimal. We conducted the WISH (Women's Improvement of Sexual and reproductive Health) study to address this problem. Data collection took place at the Rinda Ubuzima (RU) research clinic in Kigali, Rwanda, from July 2016 to March 2017. The study was sponsored by the University of Liverpool (UoL).

The primary objective of the WISH study is to evaluate whether it is feasible to improve urogenital infection care in high risk women in Kigali, Rwanda (see 'study population' below), using point of care (POC) diagnostic testing for HIV, Trichomonas vaginalis (TV), and bacterial vaginosis (BV) in all women; POC testing for Neisseria gonorrhoeae (NG), Chlamydia trachomatis (CT), and syphilis in pregnant women and women assessed to be at high risk for these infections using a risk scoring questionnaire; and management of vaginal candidiasis, urinary tract infection (UTI), genital ulcers/inguinal buboes, and lower abdominal pain (LAP) in women reporting relevant symptoms. The secondary objectives of the study are 1) to evaluate the performance and 2) cost effectiveness of the POC tests for CT/NG, TV and BV; and 3) to obtain the opinions of stakeholders (clinicians, programme implementers and policymakers) about the potential improvement of urogenital infection care in Rwanda as well as 3b) the potential roll-out of novel vaginal microbicides and multipurpose prevention technologies for HIV and pregnancy prevention as soon as efficacious products become available. This statistical analysis plan (SAP) describes the statistical analyses to be undertaken to achieve the primary objective and the first secondary objective (POCT performance), as well as some related exploratory analyses. The other secondary objectives will be analysed separately.

Primary objectives	Primary endpoints

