Women heard about the study during recruitment activities (recruitment meetings organised by RU staff, leaflets) or word of mouth. From 4 July 2016 to 2 September 2016, RU staff conducted all recruitment activities with the help of three Community Mobilisers (two were former female sex workers; one was a community organizer), as had been done previously in many RU studies. They referred high risk women to recruitment sessions in the community (conducted by RU staff) and handed out leaflets. However, this method attracted too many women who tested positive on the risk scores (mostly because many of them were sex workers). From 5 September 2016 until the week of 13 March 2017, RU staff no longer worked with the Community Mobilisers, but instead, performed the following recruitment activities: providing information and recruitment leaflets at non-governmental women's organizations (such as women's cooperatives), monthly umuganda community meetings, district hospitals, local health centers, pharmacies, and at a local family planning clinic. Earlier participants from the WISH study (especially testing negative on risk scores) were also encouraged to refer friends and family. These new strategies did indeed attract fewer women who tested positive on the risk scores. The numbers of women who were approached (at a meeting, by leaflet, or by word-of-mouth); subsequently did or did not attend the RU clinic for a Main Visit; and did or did not proceed to the informed consent procedures are not known. Data were only collected from women who attended the RU clinic after they had given informed consent.

Participants were allowed to voluntarily withdraw from the study for any reason at any time. The PI was also allowed to discontinue participants (for example, if this was deemed in the best interest of the participant). The reason(s) for withdrawal or discontinuation were recorded in the participant's records.

Participant disposition	N = 705	
N women enrolled	705	
N women excluded by PI at the Main Visit	0	
N women who completed their Main Visit	705	
N women who did not complete their Main Visit	0	
N women who withdrew their informed consent after Enrolment	0	
Participant disposition	n (%) N = 705	
N Additional Visits attended		
N women who attended one Additional Visit		
N women who attended multiple Additional Visits		
Reasons for Additional Visits ¹ :		
 To withdraw informed consent 		

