In the table below, we report the spontaneously and structurally reported symptoms, as well as the overlap in answers between the two questions. Each column contains n (% of 705).

Urogenital symptoms	Sponta-	Structural	Spontaneous but	Structural but
n (% of 705) in each column ¹	neous total	total	not structural	not spontaneous
Any reported				
Burning when passing urine				
Frequent urination/urge				
Blood in urine				
Genital burning				
Genital itching				
Postcoital/intermenstrual bleeding				
Pain during sex				
Lower abdominal pain				
Unusual VDS, curdlike				
Unusual VDS, offensive smell				
Unusual VDS, other ²				
Ulcers/blisters/sores genital/anal				
Warts genital/anal				
Swelling/bubo inguinal area				
Other ³				

Abbreviations: VDS = vaginal discharge syndrome

1. May total to more than 100% because the participant could report multiple symptoms.

2. These will be described in a footnote.

3. Additional categories may be added on to this list if certain other symptoms were mentioned frequently. Symptoms that were infrequently reported will be described in a footnote.

Other urogenital symptom-related questions	
	N = 705
Already receiving treatment for her current symptoms by another medical doctor or nurse	
Already took traditional medicine for her current symptoms	
At least one of the symptoms is ongoing	
At least one of participant's male partners has symptoms of urethritis (this question was	
asked because it is part of the Rwandan STI guidelines)	
- Yes	
- No	
- Does not know	
- NA	
At least one of participant's male partners has symptoms of swelling or tumefaction of the	
scrotum that did not start all of a sudden (this question was asked because it is part of the	
Rwandan STI guidelines)	
- Yes	
- No	
- Does not know	
- NA	

Abbreviations: IQR = interquartile range; NA = not applicable

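### SAP 7.2 declares recruitment of asymptomatic and out-of-care women feasible before symptom status is tabulated; clinic non-attendance was not measured

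*SAP*

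**What the plan says.** SAP 1.1 frames the aim as an open question: "The primary objective of the WISH study is to evaluate whether it is feasible to improve urogenital infection care in high risk women". The introduction to SAP section 7 puts it differently: "To show it is possible to implement improved urogenital infection care service, in this section, we will report M&E indicators". It sets no criterion. SAP 7.2 gives the enrolment total and period, lists difficulties noted by the outreach manager and the principal investigator, and concludes that "we have shown it is feasible to recruit women who are asymptomatic, or who have symptoms but who have not presented to local health" clinics. The sentence after it says the WISH experience shows that good counselling and the support of community mobilisers and authorities are essential for reaching women at (high) risk of STIs.

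The recruitment record is in SAP section 2. Mobilisers helped from 4 July to 2 September 2016. From 5 September, "RU staff no longer worked with the Community Mobilisers", because that route had brought in too many women positive on the risk scores. Information and leaflets were then offered at women's organisations, community meetings, "district hospitals, local health centers, pharmacies, and at a local family planning clinic", and this ran to the week of 13 March 2017. Section 2 also covers the numbers approached, those who then came to the clinic or stayed away, and those who "did or did not proceed to the informed consent procedures are not known".

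The indicators closest to the claim are in SAP 4.1. One is the table of spontaneously and structurally reported symptoms. The other is the row "Already receiving treatment for her current symptoms by another medical doctor or nurse". Both are blank shells.

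**The concern.** Blank shells are normal in an analysis plan. The difficulty is that a conclusion resting on those shells is already written in the past tense. It names two groups, asymptomatic women and symptomatic women outside local care, and would read the same whatever the shells turn out to show. If it passes into the report, readers planning a roll-out could take it as a finding that the service reaches women whom clinics miss. The study can describe the symptoms and current treatment of the women who enrolled. It cannot say what share of women approached would come, or whether symptomatic participants had already been to a clinic.

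**Working it through.** There is no planned calculation to reproduce. The protocol calls the primary objective descriptive, and neither document sets a success threshold. The check is what each available figure can support.

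**1. Total accrual.** Inputs: 705 enrolled (SAP 7.2); capacity estimate of 500 to 700 women in one year (protocol 4.3).
- 705/500 = 1.41; 705/700 = 1.007.
- 4 July 2016 to 13 March 2017 is 252 days, or 36.0 weeks; 705/36.0 = 19.6 women per week.

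Total recruitment met the estimate in less than a year. That part of the feasibility statement is sound.

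**2. Asymptomatic women.** The relevant count is the complement of the any-symptom row in SAP 4.1, once for the open question and once for the read-out list. Neither is filled in, so on the text alone the share could lie anywhere from 0 to 100% of 705. The data can settle it with useful precision. The 95% half-width is 1.96 × √(p(1−p)/705), with p assumed for illustration:

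| assumed p | half-width (percentage points) |
|---|---|
| 10% | 2.2 |
| 25% | 3.2 |
| 50% | 3.7 |

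**3. Symptomatic women who had not presented to clinics.** The nearest items are:
- treatment of current symptoms by another doctor or nurse (SAP 4.1);
- use of traditional medicine for current symptoms (SAP 4.1);
- antibiotic or antifungal use, current or in the previous two weeks (SAP section 3).

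None records a clinic visit for the current symptoms. A woman may have attended and received nothing, or attended and finished treatment. No planned table crosses symptoms with care-seeking. Treatment for an STI in the previous 12 months was one of two routes to eligibility (SAP 1.2), and later recruitment included health facilities. Some participants may therefore have been in contact with care.

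**4. Uptake.** Uptake is 705 divided by the number approached, which is unknown. For assumed numbers approached of 1,000, 2,000 or 5,000 (no figure is in the documents), it would be 70.5%, 35.2% or 14.1%.

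**5. Mobilisers.** Counting days inclusively, and taking the last week to end on Friday 17 March 2017:
- with mobilisers, 4 July to 2 September 2016: 61 days;
- without, 5 September 2016 to 17 March 2017: 194 days;
- 194/(61 + 194) = 194/255 = 76%.

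All women enrolled in either period met the definition of high risk in SAP 1.2. Women at high risk in that sense were therefore recruited without mobilisers for about three quarters of the recruiting time. The documents do not give the number of women enrolled in each period, so 76% is a share of days, not of participants.

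**The case against.** The strongest reply is that 7.2 is a narrative of field experience, written after enrolment closed, and not a decision rule. The objective is descriptive, so there is no test to bias. The SAP already schedules the symptom counts and openly says the numbers approached are unknown. The listed challenges give some anecdotal basis for care avoidance, and receiving a leaflet at a health facility is not the same as presenting there with symptoms. All of this stands, and it limits the point to wording and reporting. It does not supply the missing measurement. One of the listed challenges even concerns women who do not return to a clinic because symptoms persisted, which implies an earlier visit.

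On mobilisers, the reply is partly right. They were dropped for attracting too many score-positive women, so they did reach women at higher risk, and 7.2 ties its remark to reaching such women. What does not follow from the record is that they were essential.

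A reader might infer more than the documents support:
- That 7.2 states the primary feasibility conclusion. It concerns recruitment only; the objective is whether care can be improved using point-of-care testing.
- That nothing had been tabulated. The disposition counts in section 2 (705 enrolled, 705 completing the Main Visit, no exclusions or withdrawals) and the inputs table in 7.1 are filled in.
- That the recruitment record refutes the feasibility sentence. It leaves the sentence unsupported.
- That the sentence contradicts SAP 5.2, where all symptomatic women are assumed to have sought local care. That is a stated hypothetical for reconstructing syndromic management, not a finding.

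**Conclusion.** The point holds as a minor one. SAP 7.2 states a recruitment-feasibility conclusion, one part of the primary feasibility objective, ahead of the indicators that would support it. Enrolment of 705 supports total accrual only. The claim about asymptomatic women is premature but can be checked to within about 3.7 percentage points. The claim about symptomatic women outside local clinics cannot be checked from the items listed. The mobiliser sentence is in partial tension with section 2. The 76% rests on inclusive calendar days and an end date of 17 March 2017; ending on 13 March instead gives 190/251, also 76%. No sample size, test or planned estimate changes.

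**What to change.** In SAP 7.2, replace the feasibility sentence with results from variables already collected:
- n/705 (95% CI) reporting no symptoms, separately for the spontaneous and structured questions, noting that both cover the present and the past two weeks;
- n/705 (95% CI) with symptoms and not already receiving treatment for them from another doctor or nurse.

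State that these are proportions of enrolled women, that uptake cannot be estimated, and that non-presentation to clinics was not measured. Reword the mobiliser sentence to match section 2: mobilisers brought in more score-positive women, and recruitment continued without them from 5 September 2016. In the introduction to section 7, replace the opening "To show it is possible to implement improved urogenital infection care service" with wording that evaluates whether this is possible, in line with SAP 1.1.

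The cost is a few sentences, confidence intervals and one extra cross-tabulation. No new data are needed. The downside is a less favourable feasibility statement.
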